### 1.1. Study Objectives

Objectives for Phase 1a (Part A dose escalation only)

The primary objective(s) are:

- To assess safety and tolerability and to define the dose limiting toxicity (DLT) and maximum tolerated dose (MTD) or recommended Phase 2 dose (RP2D) of GS-1423 monotherapy in subjects with advanced solid tumors

The secondary objectives are:

- To characterize GS-1423 pharmacokinetics (PK)
- To evaluate GS-1423 immunogenicity

CCI

### 1.2. Study Design

#### Study design for Phase 1a

##### Part A – Dose escalation

Part A is a Phase 1 open-label study to evaluate the safety, tolerability, and PK profile of GS-1423 and to define the DLT and MTD or RP2D of GS-1423 monotherapy in subjects with advanced solid tumors.

In Part A, an accelerated titration design schema will be used by enrolling 1 subject each at the first 2 dose levels of 0.3 mg/kg and 1 mg/kg, followed by a 3+3 dose escalation design (Table 1). At the first 2 dose levels of 0.3 mg/kg and 1 mg/kg, if 2 or more drug-related adverse events (AEs) of Grade 2 or higher or at least 1 DLT are observed during the 28-day DLT observation period, the 3+3 escalation scheme will be used at that dose and subsequent doses. Each subject will stay on the dose level and schedule assigned at study entry. GS-1423 will be administered on Day 1 of each 2-week cycle (Q2W) for up to 1 year or until any progressive disease (PD) or unacceptable toxicity. The starting dose was selected to be 0.3 mg/kg derived from minimally anticipated biologic effect level (MABEL). A Safety Review Team (SRT) will be established to assess safety and decide on dose escalation.

[figure not shown]
**Table 1. Phase 1a Part A GS-1423 Dose Levels and Cohorts**

Cohort	No. of Subjects	Escalation Type	Dose of GS-1423 (mg/kg)
1 (starting dose)	1 or 3-6	Accelerated titration	0.3
2	1 or 3-6	Accelerated titration	1
3	3-6	3+3	3
4	3-6	3+3	10
5	3-6	3+3	20
6	3-6	3+3	30
7	3-6	3+3	45

[figure not shown]
Note: An additional 6 subjects may be enrolled at a dose level at or below maximum tolerated dose to obtain additional safety, pharmacokinetics, and CCI [REDACTED] information. Gilead may choose not to enroll any cohort if it is deemed unnecessary.

The initial block of each dose in 3+3 escalation scheme consists of 3 subjects. Dose escalation will occur if no subjects experience a DLT during the first 28 days of study drug dosing. If 2 or more subjects experience DLTs within the first 28 days, dose de-escalation to a lower dose will occur. If 1 of the first 3 evaluable subjects enrolled has a DLT within the first 28 days, then 3 additional subjects will be enrolled at the same dose level. If no DLTs are observed in the additional 3 subjects, dose escalation will occur. If a DLT occurs in  $\geq 2$  subjects in the total cohort of 6 subjects, the MTD will be deemed to be exceeded, and the prior dose level will be evaluated to determine the MTD by increasing enrollment to 6 subjects. If the prior dose level was already deemed to be safe (ie, 0 or 1 DLT) and enrolled 6 subjects, then it will be defined as the MTD. The MTD is the highest dose level with an incidence of DLTs of 0 or 1 out of 6 subjects during the first 28 days of study drug dosing. A minimum of 6 subjects need to be treated at a dose level before this dose level can be deemed as the MTD. A subject who fails to receive all GS-1423 treatments or fails to complete all safety assessments in the DLT period for reasons other than DLT will be replaced.

**Figure 1.** Accelerated Dose Escalation Scheme

**Figure 2. 3+3 Dose Escalation Scheme**

**Legend:** DLT=dose limiting toxicity; MTD=maximum tolerated dose

Note: if MTD is attained at the 1st dose level, discussion with investigators and medical monitor to change dose or schedules in a protocol amendment

Starting at Cohort 4 (10 mg/kg), if no DLT is observed during the 28-day DLT observation period in the first 3 subjects, 3 additional subjects may be enrolled at the respective dose level to obtain more safety, PK, and CCI data. If  $\geq 2$  subjects have experienced DLTs in the last 3 (of 6) subjects, dose escalation will halt and up to 3 additional subjects will be enrolled at the preceding dose level (if there were only 3 subjects in that cohort) for DLT assessment. If 6 subjects were already evaluated, the preceding dose level will be considered as MTD.

### **Efficacy Assessment Schedule**

For Phase 1a Part A, tumor response assessment will be performed per RECIST 1.1 at baseline ( $\leq 28$  days prior to first dose), every 6 weeks ( $\pm 7$  days) for the first 24 weeks from the first treatment dose and then every 12 weeks thereafter until PD is assessed by investigator, initiation of new line of therapy, or 1 year after first treatment dose, whichever occurs first. Any CR or PR should be confirmed by CT or MRI scan no less than 28 days after initial assessment. The investigator may perform scans in addition to a scheduled study scan for medical reasons or if PD is suspected.

The Schedule of Assessments is located in [Appendix 1](#).

### **1.3. Sample Size and Power**

#### **Phase 1a Part A**

Assuming that up to 7 planned dose levels for escalation will be tested with up to 6 subjects per dose level (42 subjects for escalation) and 10% of subjects are not evaluable, and 6 additional subjects may be enrolled at a dose level at or below MTD to obtain additional safety, PK, and CCI information, up to 53 subjects will be enrolled.

## **2. TYPE OF PLANNED ANALYSIS**

### **2.1. Interim Analyses**

#### **2.1.1. Dose Escalation Analysis**

For the purpose of making the decision to escalate to the next dose level/cohort, interim analyses of relevant safety and PK (if available) data will be conducted by Gilead after all subjects in each cohort have completed dosing and the 28-day DLT observation period. Safety assessments (ie, AEs, ECG, and laboratory results) will be displayed by dose level/cohort to facilitate the decision to dose escalate.

### **2.2. Final Analysis**

The final analysis will be performed after all subjects have completed or discontinued from the study, outstanding data queries have been resolved or adjudicated as unresolvable, and the data have been cleaned and finalized. The final analysis of this study will include Phase 1a Part A only.

### **3. GENERAL CONSIDERATIONS FOR DATA ANALYSES**

Analysis results will be presented using descriptive statistics. For categorical variables, the number and percentage of subjects in each category will be presented; for continuous variables, the number of subjects (n), mean, standard deviation (StD) or standard error (SE), median, first quartile (Q1), third quartile (Q3), minimum, and maximum will be presented.

By-subject listings will be presented for all subjects in the All Enrolled Analysis Set and sorted by subject ID number, visit date, and time (if applicable). Data collected on log forms, such as AEs, will be presented in chronological order within the subject. The treatment group to which subjects were initially assigned will be used in the listings. Age, sex at birth, race, and ethnicity will be included in the listings, as space permits.

#### **3.1. Analysis Sets**

Analysis sets define the subjects to be included in an analysis. Analysis sets and their definitions are provided in this section. The analysis set will be identified and included as a subtitle of each table, figure, and listing.

For each analysis set, the number and percentage of subjects eligible for inclusion, will be summarized by dose cohort.

A listing of reasons for exclusion from analysis sets will be provided by subject.

##### **3.1.1. All Enrolled Analysis Set**

All Enrolled Analysis Set includes all subjects who received a study subject identification number in the study after screening.

The All Enrolled Analysis Set will be used for subject enrollment summary and for data listings, unless otherwise specified.

##### **3.1.2. Full Analysis Set**

The Full Analysis Set (FAS) includes all enrolled subjects who were administered any amount of GS-1423. This is the primary analysis set for efficacy analyses.

##### **3.1.3. Safety Analysis Set**

The Safety Analysis Set includes all enrolled subjects who were administered any amount of GS-1423. This is the primary analysis set for safety analyses.

##### **3.1.4. Dose-Limiting Toxicity (DLT) Analysis Set**

The DLT Analysis Set includes all subjects in the Safety Analysis Set who complete all study treatment and have safety assessments through the protocol specified DLT assessment window, Day 28, inclusive, or have experienced a DLT prior to Day 28.

During the DLT observation window, if a subject was not administered both of first 2 GS-1423 doses for reasons other than DLT, another subject was to be enrolled at the same dose level for replacement. Subjects who are replaced but received at least 1 dose of study drug will be included in the Safety Analysis Set and not in the DLT Analysis Set.

The DLT Analysis Set will be used for analyses related to DLT in Part A of Phase 1a.

### **3.1.5. Pharmacokinetic Analysis Set**

The Pharmacokinetic (PK) Analysis Set will include all subjects in the Safety Analysis Set who have at least 1 nonmissing postdose concentration value reported by the PK laboratory. This is the primary analysis set for all PK analyses.

### **3.1.6. Immunogenicity Analysis Set**

The Immunogenicity Analysis Set will include all subjects in the Safety Analysis Set who have at least 1 nonmissing postdose antidrug antibody (ADA) status reported. This is the primary analysis set for all immunogenicity analyses.

## **3.2. Subject Grouping**

For analyses based on the Full Analysis Set (FAS), subjects will be grouped according to the treatment to which they were assigned. For analyses based on the Safety Analysis Set, subjects will be grouped according to the actual treatment received. The actual treatment received will differ from the assigned treatment only when their actual treatment differs from the assigned treatment for the entire treatment duration.

For the PK Analysis Set, subjects will be grouped according to the actual treatment they received.

In Phase 1a Part A, The subjects will be grouped by cohorts (dose levels):

Cohort 1: 0.3 mg/kg

Cohort 2: 1 mg/kg

Cohort 3: 3 mg/kg

Cohort 4: 10 mg/kg

Cohort 5: 20 mg/kg

Cohort 6: 30 mg/kg

Cohort 7: 45 mg/kg

## **3.3. Strata and Covariates**

This study does not use a stratified randomization schedule when enrolling subjects. No covariates will be included in efficacy and safety analyses.

### **3.4. Examination of Subject Subgroups**

There are no prespecified subject subgroupings for efficacy and safety analyses.

### **3.5. Multiple Comparisons**

There are no adjustments for multiplicity in this study.

### **3.6. Missing Data and Outliers**

#### **3.6.1. Missing Data**

In general, missing data will not be imputed unless methods for handling missing data are specified. Exceptions are presented in this document.

For missing last dosing date of study drug, imputation rules are described in Section 4.2.1.1. The handling of missing or incomplete dates for the completion of last prior anti-cancer therapy is in Section 5.3, for the start date of new anti-cancer therapy is in Section 6.1.3, for date of death in Section 6.1.4, for AE onset in Section 7.1.5.2, and for prior and concomitant medications in Section 7.4.

#### **3.6.2. Outliers**

Outliers will be identified during the data management and data analysis process, but no sensitivity analyses will be conducted. All data will be included in the data analysis.

### **3.7. Data Handling Conventions and Transformations**

In general, the subject's age collected at Day 1 (in years) will be used for analyses and presented in listings. If age at Day 1 is not available for a subject, then age derived based on date of birth and the Day 1 visit date will be used instead. If an enrolled subject was not dosed with any study drug, the enrollment date will be used instead of the Day 1 visit date. For screen failures, the date the first informed consent was signed will be used for the age derivation. If only the birth year is collected on the CRF, "01 July" will be used for the unknown birth day and month for the purpose of age calculation.

Non-PK data that are continuous in nature but are less than the lower limit of quantitation (LOQ) or above the upper LOQ will be imputed as follows:

- A value that is 1 unit less than the LOQ will be used to calculate descriptive statistics if the datum is reported in the form of “ $< x$ ” (where  $x$  is considered the LOQ). For example, if the values are reported as  $< 50$  and  $< 5.0$ , values of 49 and 4.9, respectively, will be used to calculate summary statistics. An exception to this rule is any value reported as  $< 1$  or  $< 0.1$ , etc. For values reported as  $< 1$  or  $< 0.1$ , a value of 0.9 or 0.09, respectively, will be used to calculate summary statistics.

- A value that is 1 unit above the LOQ will be used to calculate descriptive statistics if the datum is reported in the form of “ $> x$ ” (where x is considered the LOQ). Values with decimal points will follow the same logic as above.
- The LOQ will be used to calculate descriptive statistics if the datum is reported in the form of “ $\leq x$ ” or “ $\geq x$ ” (where x is considered the LOQ).

If methods based on the assumption that the data are normally distributed are not adequate, analyses may be performed on log-transformed data or nonparametric analysis methods may be used, as appropriate.

Sparse PK concentration values that are below the limit of quantitation (BLQ) will be presented as “BLQ” in the data listing.

Natural logarithm transformation will be used for analyzing concentrations and PK parameters in intensive PK samples. Concentration values that are BLQ will be presented as “BLQ” in the concentration data listing. Values that are BLQ will be treated as 0 at predose time points, and at postdose time points for summary purposes. The following conventions will be used for the presentation of summary and order statistics for intensive PK concentrations:

- If at least 1 subject has a concentration value of BLQ for the time point, the minimum value will be displayed as “BLQ.”
- If more than 25% of the subjects have a concentration data value of BLQ for a given time point, the minimum and Q1 values will be displayed as “BLQ.”
- If more than 50% of the subjects have a concentration data value of BLQ for a given time point, the minimum, Q1, and median values will be displayed as “BLQ.”
- If more than 75% of the subjects have a concentration data value of BLQ for a given time point, the minimum, Q1, median, and Q3 values will be displayed as “BLQ.”
- If all subjects have concentration data values of BLQ for a given time point, all order statistics (minimum, Q1, median, Q3, and maximum) will be displayed as “BLQ.”

PK parameters that are BLQ will be excluded from log transformation or statistical model fitting.

### **3.8. Analysis Visit Windows**

#### **3.8.1. Definition of Study Day**

Study day will be calculated from the first dosing date of study drug and derived as follows:

- For postdose study days: Assessment Date – First Dosing Date + 1
- For days prior to the first dose: Assessment Date – First Dosing Date

Therefore, study day 1 is the day of first dose of study drug.

### **3.8.2. Analysis Visit Windows**

The nominal visit as recorded on the CRF will be used when data are summarized by visit. Any data relating to unscheduled visits will not be assigned to a particular visit or time point. However, the following exceptions will be made:

- An unscheduled visit prior to the first dosing of study drug may be included in the calculation of the baseline value, if applicable.
- Unscheduled visits after the first dosing of study drug will be included in determining the maximum postbaseline toxicity grade.

### **3.8.3. Selection of Data in the Event of Multiple Records in an Analysis Visit Window**

Depending on the statistical analysis method, single values may be required for each analysis window. For example, change from baseline by visit usually requires a single value, whereas a time-to-event analysis would not require 1 value per analysis window.

If multiple valid, nonmissing measurements exist in an analysis window, records will be chosen based on the following rules if a single value is needed:

- For baseline, the last nonmissing value on or prior to first dosing date of study drug will be selected, unless specified differently. If there are multiple records with the same time or no time recorded on the same day, the baseline value will be the average of the measurements for continuous data, or the measurement with the lowest severity (eg, normal will be selected over abnormal for safety electrocardiogram [ECG] findings) for categorical data.

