6.2.6. Electrocardiogram

A standard 12-lead ECG will be performed using local standard procedures at screening and as specified in [Appendix 2](#). For subjects in Cohorts 5 through 10, a triplicate ECG will be performed at Cycle 1, Day 1 predose, at end of infusion, at 24 hours postdose (Day 2), and 168 hours postdose (Day 8). Clinically significant abnormal findings at screening should be recorded as medical history.

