8.4. Data Handling Conventions

By-subject listings will be created for important variables from each eCRF module. Summary tables for continuous variables will contain the following statistics: N (number in population), n (number with data), mean, standard deviation, 90% confidence intervals (CIs) on the mean, median, minimum, and maximum. Summary tables for categorical variables will include: N, n, percentage, and 90% CIs on the percentage. Unless otherwise indicated, 90% CIs for binary variables will be calculated using the binomial distribution (exact method) and will be 2-sided. Data will be described and summarized by dose level/cohort, analysis set, and time point. As appropriate, changes from baseline to each subsequent time point will be described and summarized. Similarly, as appropriate, the best change from baseline during the study will also be described and summarized. Graphical techniques (ie, waterfall plots, Kaplan-Meier [KM] curves, line plots) may be used when such methods are appropriate and informative.

The baseline value used in each analysis will be the last (most recent) pretreatment value. Data from all sites will be pooled for all analyses. Analyses will be based upon the observed data unless methods for handling missing data are specified. If there is a significant degree of non-normality, analyses may be performed on log-transformed data or nonparametric tests may be applied, as appropriate.

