### 7.3. Body Weight, Body Mass Index and Vital Signs

Descriptive statistics will be provided by dose cohort for body weight, body mass index (BMI) and vital signs as follows:

- Baseline value
- Postbaseline maximum value
- Postbaseline minimum value
- Change and percentage change from baseline to postbaseline maximum value
- Change and percentage change from baseline to postbaseline minimum value

A baseline value will be defined as the last available value collected on or prior to the date/time of first dose of study drug. Weight, BMI and each vital signs measurement (including

temperature, pulse, respiratory rate, and blood pressure) will be summarized. Change from baseline to a postbaseline visit will be defined as the postbaseline value minus the baseline value.

In the case of multiple values in an analysis window, data will be selected for analysis as described in Section 3.8.3. No formal statistical testing is planned.

A by-subject listing of vital signs will be provided by subject ID number and visit in chronological order. Body weight and BMI will be included in the vital signs listing, if space permits. If not, they will be provided separately.

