- a All subjects who discontinue treatment will have at least one 30-Day Follow-up Visit 30 days (± 7 days) from last treatment dose. Subjects who discontinue due to PD and/or start of a new line of therapy will then enter the Survival Follow-up Period for up to 12 months for survival status. Subjects who have discontinued treatment due to reasons other than PD and/or start of a new line of therapy will be in Posttreatment Follow-up for up to approximately 12 months from last treatment dose or until PD and/or start of a new line of therapy. Every effort should be made to collect subject information on the start of new anticancer therapy, PD, and death.
- b Treatment administration and associated procedures for that visit may be delayed for treatment-related AEs beyond the window and subsequent schedule adjusted accordingly.
- c After informed consent, but prior to initiation of study medication, the following types of events should be reported on the case report form (CRF/eCRF): all SAEs and AEs related to protocol-mandated procedures.
- d 72-hour window for C1D1 physical examination, safety labs, and ECOG performance status collection.
- e Vital signs will only be measured while subject is in seated or semi-recumbent position. Height only collected at screening. Phase 1a and Phase 1b (Cohort 2): Vital signs are to be measured prior to each infusion commencing, at the end of each infusion, and for the first 2 cycles, 1 hour (± 15 minutes) after the end of the GS-1423 infusion. Thereafter, the final vital signs can be taken 30 minutes (-10/+20 minutes) after the end of each GS-1423 infusion. Subjects will remain in the clinic under close supervision for the duration of this monitoring period. Phase 1b (Cohort 1): Additional vital signs for subjects being administered the mFOLFOX6 regimen will be measured as per standard institutional guidelines.
- f 12-lead ECG on Cycle 1 Day 1, before and 2 hours (-10/+20 minutes) after GS-1423 administration; on subsequent cycles, 12-lead ECG will be collected every odd cycle, on Day 1, at end of GS-1423 infusion(-10/+20 minutes), or as indicated. For subjects in Cohorts 5 through 8 and Cohort 10, a triplicate ECG will be performed at Cycle 1, Day 1 predose, at end of infusion, at 24 hours postdose (Day 2), and 168 hours postdose (Day 8).

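### SAP 3.8.3 ties baseline to the first dosing date and not the time of dose, so a post-infusion Day 1 ECG can become the baseline of the ECG shift table

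*SAP*

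**What the plan says.** The general baseline rule is in SAP 3.8.3: "For baseline, the last nonmissing value on or prior to first dosing date of study drug will be selected, unless specified differently". When several records fall on the same day with the same time or with no time, continuous values are averaged. For categorical data the rule takes "the measurement with the lowest severity (eg, normal will be selected over abnormal for safety electrocardiogram [ECG] findings) for categorical data".

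The ECG schedule is in footnote f of SAP Appendix 1. It calls for a "12-lead ECG on Cycle 1 Day 1, before and 2 hours (-10/+20 minutes) after GS-1423 administration". For a group that in Part A means Cohorts 5 to 7, it adds that "a triplicate ECG will be performed at Cycle 1, Day 1 predose, at end of infusion" and on Days 2 and 8. Protocol 6.2.6 gives the same triplicate schedule ("For subjects in Cohorts 5 through 10, a triplicate ECG will be performed at Cycle 1, Day 1 predose, at end of infusion") and does not list a 2-hour ECG for those cohorts.

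Protocol 8.4 defines baseline differently: "The baseline value used in each analysis will be the last (most recent) pretreatment value". SAP 7.3 uses the time of dose for weight, BMI and vital signs: "the last available value collected on or prior to the date/time of first dose of study drug". SAP 7.5, 7.5.1 and 7.5.2 contain no baseline definition. SAP 7.5.1 plans a shift table by dose cohort that sets each subject's worst ECG assessment on study against baseline. The levels are normal, abnormal but not clinically significant, and abnormal and clinically significant, with a separate missing category.

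**The concern.** On the day of first dose a subject has ECGs both before and after the infusion. A rule that accepts anything up to and including that date admits both, and taking the last one selects the post-infusion record. SAP 3.8.3 names safety ECG findings as its own example, so it is clearly meant to govern them. Its exception for cases specified differently is not used anywhere in the ECG section.

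At stake is the one planned ECG summary that compares on-treatment findings with baseline. SAP 7.5 says the ECG analyses are there to pick up meaningful changes. A baseline taken after first exposure can hide the earliest such change, or make a pre-existing abnormality look like a drug effect.

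**Working it through.** The plan states no figure to reproduce. The check applies each baseline rule to the scheduled records and compares the results.

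**1. ECG records on the first dosing date (SAP Appendix 1, footnote f; protocol 6.2.6)**

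| Cohorts | Before infusion | After infusion, same date | Post-infusion time points |
|---|---|---|---|
| 1 to 4 | predose | 2 hours | 1 |
| 5 to 7, triplicate replaces the 2-hour ECG | predose | end of infusion | 1 |
| 5 to 7, triplicate adds to it | predose | end of infusion and 2 hours | 2 |

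Footnote f does not say which of the last two rows applies. It makes no difference here, because the minimum is 1 in every cohort. The general schedule note that assessments precede treatment does not help, since it yields where a footnote indicates otherwise, as footnote f does.

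**2. Record selected by each rule**

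- SAP 3.8.3, times recorded: the last post-infusion ECG of Day 1.
- SAP 3.8.3, no times recorded: the least severe of all Day 1 ECGs, predose and post-infusion together.
- Protocol 8.4: the Day 1 predose ECG, or the screening ECG if the predose one is missing.

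The documents do not say whether ECG times are captured, so both SAP branches are kept.

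**3. Effect on the baseline level**

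Three levels at predose and three after infusion give 3 × 3 = 9 combinations. Three agree and six differ. With timed records the SAP baseline is wrong in all six. With untimed records it is wrong in the three where the post-infusion ECG is the less severe.

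**4. Effect on the shift table**

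N = normal, NCS = abnormal not clinically significant, CS = abnormal clinically significant. Sequences run predose / Day 1 post-infusion / later.

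| Sequence | Correct shift | SAP rule, timed, Day 1 postdose counted as on study | SAP rule, timed, not counted | SAP rule, untimed |
|---|---|---|---|---|
| N / CS / N | N to CS | CS to CS | CS to N | baseline N (correct) |
| NCS / CS / NCS | NCS to CS | CS to CS | CS to NCS | baseline NCS (correct) |
| CS / N / CS | CS to CS | N to CS | N to CS | N to CS |

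The first two rows lose a change that followed the first infusion. The third creates a new shift that did not occur.

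**5. Scale**

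SAP 1.3 plans up to 53 Part A subjects: 42 / 0.9 = 46.7, rounded up to 47, plus 6 = 53. Each has at least one post-infusion ECG scheduled on the first dosing date. One reclassified subject is 1/3 = 33.3 percentage points of a cohort of 3 and 1/6 = 16.7 of a cohort of 6.

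**The case against.** The best defence is that a predose baseline is plainly intended. Protocol 8.4 fixes baseline for every analysis, the SAP is based on that protocol, and SAP 7.8 declares no departure from the protocol's safety analyses. SAP 3.8.3 can then be read as a way of choosing among records already eligible under protocol 8.4. SAP 3.8.2 points the same way: "An unscheduled visit prior to the first dosing of study drug may be included in the calculation of the baseline value, if applicable", while unscheduled visits after first dosing count toward the worst postbaseline toxicity grade. It would be odd to treat an unscheduled postdose record as postbaseline and a scheduled one as baseline.

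The intent is probably as described, but none of this overrides the rule. The SAP 3.8.2 sentences cover unscheduled visits only. SAP 7.3 covers weight, BMI and vital signs only, and shows that the authors had the right wording and did not apply it to ECGs. SAP 7.8 is a general statement. SAP 3.8.3 is the only general baseline rule in the readable text, and a programmer following it would select the wrong record.

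The objections about size do stand:

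- The table is descriptive, with no formal testing.
- ECG assessments and QTcF are listed by subject, so the data can be recovered.
- The percentage of subjects with a clinically significant abnormal ECG (protocol 8.1.3) needs no baseline.
- Laboratory samples are by default drawn before dosing, and vital signs use date and time, so neither is affected.
- The 53 is a planned ceiling that includes a 10% allowance for non-evaluable subjects and 6 optional subjects.
- The worst result on study naturally includes Day 1 postdose ECGs, so the column above where they are not counted is the less likely reading.

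**Conclusion.** The concern holds. As written, SAP 3.8.3 can give the SAP 7.5.1 shift table a post-infusion baseline, contrary to protocol 8.4. With timed records this happens for every subject whose scheduled Day 1 post-infusion ECG was done. With untimed records it matters when the post-infusion ECG is less severe than the predose one.

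The table changes only for subjects whose two assessments differ. The documents give neither ECG times nor abnormality rates, so that number is unknown and could be zero. In cohorts of 3 or 6, one subject is enough to move a cell by 33.3 or 16.7 percentage points.

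The conclusion rests on the literal text and on no ECG baseline being defined in the readable parts of SAP 7.5. It reaches one descriptive table in a synoptic report covering Part A only. It should be corrected because the rule itself is wrong, but it does not undermine the trial's other safety results.

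**What to change.** In SAP 3.8.3, or in SAP 7.5 for ECGs alone, define baseline as the last nonmissing value before the date and time of first dose. If the time is missing, use the record scheduled as predose. This brings the SAP into line with protocol 8.4 and close to its own SAP 7.3. The tie rule should then apply only among predose records.

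As a smaller clarification, state in SAP 7.5.1 that Cycle 1 Day 1 ECGs taken at end of infusion or at 2 hours are postbaseline and count toward the worst outcome.

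The cost is two SAP sentences and a programming change. No new data are needed.
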